16.1.3 Serious Adverse Events and Serious Adverse Device Effects

An AE or ADE is considered a **Serious** Adverse Event (SAE) or **Serious** Adverse Device Effects (SADE) if, in the view of either the Investigator or the Sponsor, it:

- Results in death.
- Is life-threatening (*NOTE:* The term “life-threatening” in the definition of “serious” refers to an event/reaction in which the subject was at risk of death at the time of the event/reaction; it does not refer to an event/ reaction which hypothetically might have caused death if it were more severe).
- Requires in subject hospitalization or results in prolongation of existing hospitalization.
- Results in persistent or significant incapacity or substantial disruption of the ability to conduct normal life functions.
- Is a congenital anomaly/birth defect.
- Is a medically important event or reaction.

Medical and scientific judgment should be exercised in deciding whether other situations should be considered serious such as important medical events that might not be immediately life

CONFIDENTIAL AND PROPRIETARY

This document contains information that is confidential and proprietary to Smith & Nephew PLC and Smith & Nephew, Inc. and is intended for use only by Smith & Nephew and its manufacturer. It shall not be reproduced or copied in whole or in part, nor shall the contents be disclosed by any means without prior written permission from Smith & Nephew, nor shall anyone make any use of it that is contrary to the expressed or implied wishes of Smith & Nephew.

Study Protocol—Device	
PMCF Study on PEEK Suture Anchors for Hip Indications	Number: 2018.14.SMD.PEEK.RET.HIP
	Version: 2.0, 03 April 2019
	Page: 46 of 63

threatening or result in death or hospitalization but might jeopardize the subject or might require intervention to prevent one of the other outcomes listed in the definition above. Examples of such events are intensive treatment in an emergency room or at home for allergic bronchospasm, blood dyscrasias, or convulsions that do not result in hospitalization, or development of drug dependency or drug abuse.

16.1.4 Anticipated/Unanticipated Serious Adverse Device Effect

An Unanticipated Serious Adverse Device Effect (USADE) is a serious ADE that meets any of the above definitions but is also considered, by the Investigator, to be caused by or related to the IP, not previously identified in nature, severity or degree in the IFU.

An Anticipated Serious Adverse Device Effect (ASADE) is a serious ADE that does not meet the criteria for a USADE.

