14.4 SAFETY ANALYSES

- All safety endpoints will be summarized using the safety population. The incidence of events encountered on study will be summarized using frequencies and percentages. An overall AE table will be summarized using the overall incidence according to subjects with at least one AE; subjects with at least one AE by worst severity (mild, moderate, or severe); subjects with at least one AE by worst outcome; subjects with one AE that led to study discontinuation; subjects with at least one AE by relatedness to investigational device; SAEs; ADEs; ASADEs; USADEs and SADEs as applicable. A cumulative summary by the number of events encountered within each classification will also be summarized. The incidence of subjects reporting device deficiencies will additionally be summarized.
- Each of the AE classifications will further be summarized by event using the frequencies (n) and percentages (%) of subjects with each event as well as the cumulative events/episodes per event.
- A listing of concomitant medications will be provided by subject.

CONFIDENTIAL AND PROPRIETARY

This document contains information that is confidential and proprietary to Smith & Nephew PLC and Smith & Nephew, Inc. and is intended for use only by Smith & Nephew and its manufacturer. It shall not be reproduced or copied in whole or in part, nor shall the contents be disclosed by any means without prior written permission from Smith & Nephew, nor shall anyone make any use of it that is contrary to the expressed or implied wishes of Smith & Nephew.

Study Protocol—Device	
PMCF Study on PEEK Suture Anchors for Hip Indications	Number: 2018.14.SMD.PEEK.RET.HIP
	Version: 2.0, 03 April 2019
	Page: 42 of 63

Additional summaries of safety endpoints, if applicable, will be described in the SAP.

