16. ADVERSE EVENTS AND DEVICE DEFICIENCIES

16.1 DEFINITIONS

The categories of adverse events are shown in Table 4. The definitions for each of these categories are given in the subsequent sections (see reference within the table). All adverse events will be captured from the time of surgery through the 12-month follow-up visit.

[Intentionally left blank]

CONFIDENTIAL AND PROPRIETARY

This document contains information that is confidential and proprietary to Smith & Nephew PLC and Smith & Nephew, Inc. and is intended for use only by Smith & Nephew and its manufacturer. It shall not be reproduced or copied in whole or in part, nor shall the contents be disclosed by any means without prior written permission from Smith & Nephew, nor shall anyone make any use of it that is contrary to the expressed or implied wishes of Smith & Nephew.

Study Protocol—Device	
PMCF Study on PEEK Suture Anchors for Hip Indications	Number: 2018.14.SMD.PEEK.RET.HIP
	Version: 2.0, 03 April 2019
	Page: 44 of 63

Table 5: Categories of Adverse Events

		DEVICE- OR PROCEDURE-RELATED	
		NOT DEVICE-RELATED	
NON-SERIOUS	ADVERSE EVENT (AE)	ADVERSE DEVICE EFFECT (ADE)	
SERIOUS	SERIOUS ADVERSE EVENT (SAE)	SERIOUS ADVERSE DEVICE EFFECT (SADE)	
		ANTICIPATED	UNANTICIPATED
		ANTICIPATED SERIOUS ADVERSE DEVICE EFFECT (ASADE)	UNANTICIPATED SERIOUS ADVERSE DEVICE EFFECT (USADE)

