16.1.2 Adverse Device Effect

An Adverse Device Effect (ADE) is an adverse event that, in the opinion of the investigator, is related to the IP or the procedure.

CONFIDENTIAL AND PROPRIETARY

This document contains information that is confidential and proprietary to Smith & Nephew PLC and Smith & Nephew, Inc. and is intended for use only by Smith & Nephew and its manufacturer. It shall not be reproduced or copied in whole or in part, nor shall the contents be disclosed by any means without prior written permission from Smith & Nephew, nor shall anyone make any use of it that is contrary to the expressed or implied wishes of Smith & Nephew.

Study Protocol—Device	
PMCF Study on PEEK Suture Anchors for Hip Indications	Number: 2018.14.SMD.PEEK.RET.HIP
	Version: 2.0, 03 April 2019
	Page: 45 of 63

Not Related - An AE is considered to be not related to the use of an IP or the procedure when the effect is DEFINITELY UNRELATED or UNLIKELY to have any relationship to the use of the IP or the procedure.

Related – An AE is considered to be related to the use of an IP or the procedure when there is a POSSIBLE, PROBABLE, or DEFINITE relationship between the AE and the use of the IP or the procedure.

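### The remainder definition of ASADE labels a serious procedure-only event that is not in the IFU as anticipated

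*Combined protocol and SAP*

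**What the plan says.** Four definitions in section 16.1 of the protocol build on each other.

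- **ADE (16.1.2):** "An Adverse Device Effect (ADE) is an adverse event that, in the opinion of the investigator, is related to the IP or the procedure". Either relation is enough.
- **Seriousness (16.1.3):** an AE or ADE becomes an SAE or SADE "if, in the view of either the Investigator or the Sponsor, it" meets one of the listed criteria. No device-only condition is added at this step.
- **USADE (16.1.4):** a serious ADE with the added condition that it be "considered, by the Investigator, to be caused by or related to the IP, not previously identified in nature, severity or degree in the IFU". The procedure is not mentioned.
- **ASADE (16.1.4):** "An Anticipated Serious Adverse Device Effect (ASADE) is a serious ADE that does not meet the criteria for a USADE". Nothing requires the event to be listed anywhere.

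Table 5 places the anticipated and unanticipated boxes under SADE, and one of its headings reads "DEVICE- OR PROCEDURE-RELATED". Section 14.4 carries the labels into the results: the overall AE table includes "SAEs; ADEs; ASADEs; USADEs and SADEs as applicable", and each classification is then summarised by event.

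**The concern.** The relatedness condition narrows between ADE and USADE, from device or procedure to device only, and ASADE takes whatever is left. The label *anticipated* can therefore be earned in two ways: because the IFU identifies the event, or because the event was not attributed to the device. The second has nothing to do with expectedness.

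The affected class is within the study's scope. The safety endpoints in 12.3.3 include intra-operative events and complications, adverse events are captured from surgery onward (16.1), and 16.2 asks the investigator to judge relation to both device and procedure, so a procedure-only attribution can arise. Safety is part of the primary objective (9.1). A reader of the 14.4 table would take an ASADE to be an event already described in the labelling, and for this class that would be untrue.

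**Working it through.** The plan gives no figure to reproduce here. The check is a logical enumeration of the definitions.

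**Inputs**, for an event already judged serious:
- D = related to the IP (yes/no)
- P = related to the procedure (yes/no)
- L = identified in the IFU in nature, severity and degree (yes/no)

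**Rules as written**
- ADE = D or P (16.1.2)
- USADE = ADE and D and not L (16.1.4)
- ASADE = ADE and not USADE (16.1.4)

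**Comparison rule:** USADE uses the same base as ADE, so USADE = ADE and not L.

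| D | P | L | As written | USADE on the ADE base |
|---|---|---|---|---|
| no | no | no | SAE only | SAE only |
| no | no | yes | SAE only | SAE only |
| **no** | **yes** | **no** | **ASADE** | **USADE** |
| no | yes | yes | ASADE | ASADE |
| yes | no | no | USADE | USADE |
| yes | no | yes | ASADE | ASADE |
| yes | yes | no | USADE | USADE |
| yes | yes | yes | ASADE | ASADE |

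One of the 2 × 2 × 2 = 8 combinations differs: serious, procedure-related only, not in the IFU. It is an ADE because P holds, and a SADE because it is serious. It fails USADE because a USADE must be one that "is also considered, by the Investigator, to be caused by or related to the IP", and so it falls to ASADE. In this row L is *no*, so the anticipated label is wrong whichever base was intended for USADE.

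An event related to both device and procedure and absent from the IFU is a USADE under either rule, so the gap does not extend to it.

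No other section closes the gap. There is no separate expectedness test for ASADE and no category for unlisted procedure-only events. The relatedness breakdown in 14.4 is by relation to the investigational device, so it does not isolate procedure-only events. The sponsor's medical review in 16.2 decides on expedited reporting and is given no role in changing the ASADE or USADE label.

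**The case against.** The strongest reply is that a device-only USADE is deliberate. In a post-market device study it is coherent to reserve the unanticipated device effect for events attributed to the device, and widening it would change what the count means. This stands as far as USADE goes. A reader might infer that the USADE count is biased low, but the documents support that only if the device-or-procedure base was intended, and they do not say so. The reply does not rescue ASADE: an unlisted procedure-only event is not anticipated on either reading.

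A reader might also infer that Table 5 flatly contradicts 16.1.4. The table states no criterion for anticipated versus unanticipated, and its layout did not survive extraction, so it cannot carry that claim. The mismatch between 16.1.2 and 16.1.4 is sufficient without it.

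On size, it is tempting to assume a rate. At 1% to 3% of subjects, 240 subjects would give 2.4 to 7.2 affected and the minimum of 40 would give 0.4 to 1.2. The documents give no rate for such events, so these figures illustrate and do not estimate. The class may also be small, because possible relation counts as related (16.1.2), so a possible link to the IP takes an event out of it. The IFU texts are referenced but not reproduced, so it cannot be seen which complications they omit.

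Finally, the consequences are limited. The events remain in the AE, ADE and SADE counts, the by-event summaries keep the event term visible, and ADEs and SAEs still go to the sponsor within 24 hours and to medical review. The clinical success endpoints and the sample size do not depend on these labels. All of this stands, and it limits the point to a mislabelled category in a safety table.

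**Conclusion.** The concern holds as a defect of definition that reaches a tabulated safety result. As written, every serious event judged related to the procedure but not to the IP, and not identified in the IFU, is counted as anticipated. The ASADE count is overstated by the number of such events. The USADE count is understated by the same number only on the condition that USADE was meant to share the device-or-procedure base of 16.1.2 and the Table 5 heading. That number cannot be derived from the documents and may be zero.

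The conclusion rests on reading 16.1.2 to 16.1.4 literally and on the investigator being able to attribute an event to the procedure and not to the device, which 16.2 allows. It does not imply that any event would go unreported or unreviewed.

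**What to change.** Before database lock, when section 14 requires the SAP to be final, reconcile 16.1.2, 16.1.4 and Table 5. ASADE should require that the IFU identifies the event's nature, severity and degree, and a serious ADE not so identified should not be counted as anticipated. There are two ways to place the remaining events:

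1. Define USADE on the same IP-or-procedure base as ADE. This needs no separate relationship ratings for the classification, but it widens USADE to events not attributed to the device.
2. Keep USADE device-only and give unlisted procedure-only serious events their own line in the 14.4 table. This leaves the meaning of USADE unchanged, but it needs device and procedure relation to be distinguishable for each event.

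For option 2, use the two relationship assessments that 16.2 requires, and confirm that the CRF records them separately. The protocol does not show this: the only relatedness scale it defines, in 16.1.2, pools device and procedure. If the CRF holds a single rating, a field would have to be added.

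The cost is a rewording of 16.1.4 with matching edits to 16.1.2 and Table 5, at most one extra table line, the CRF check, and the approvals that section 19 requires for an amendment. The downside is that the unanticipated count may look slightly less favourable.

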16.1.5 Severity

The severity of every AE will be assessed by the PI or medically qualified site staff to whom the responsibility has been delegated and documented on the delegation of authority log. AE should be classified as mild, moderate, or severe, regardless of whether or not the AE are considered to be serious or non-serious. The classification should be based on the following definitions:

Mild - An event is mild if the subject is aware of, but can easily tolerate the sign or symptom.

Moderate - An event is moderate if the sign or symptom results in discomfort significant enough to cause interference with the subject's usual activities.

CONFIDENTIAL AND PROPRIETARY

This document contains information that is confidential and proprietary to Smith & Nephew PLC and Smith & Nephew, Inc. and is intended for use only by Smith & Nephew and its manufacturer. It shall not be reproduced or copied in whole or in part, nor shall the contents be disclosed by any means without prior written permission from Smith & Nephew, nor shall anyone make any use of it that is contrary to the expressed or implied wishes of Smith & Nephew.

Study Protocol—Device	
PMCF Study on PEEK Suture Anchors for Hip Indications	Number: 2018.14.SMD.PEEK.RET.HIP
	Version: 2.0, 03 April 2019
	Page: 47 of 63

Severe - An event is severe if the sign or symptom is incapacitating and results in the subject's inability to work or engage in their usual activities.

16.1.6 Device Deficiency

A Device Deficiency (DevD) is an inadequacy of a medical device with respect to its identity, quality, durability, reliability, safety or performance. DevD includes malfunctions, use errors and inadequate labelling.

16.2 REPORTING PROCEDURES

AE of any kind and DevD will be recorded in the applicable CRF and source notes. The Investigator will evaluate all AE for relationship to the device and procedure, if applicable, seriousness, and severity. ADE, SAE, and DevD will be entered into the CRF and reported to the Sponsor within 24 hours of the investigator being informed about the event (Figure 1). Applicable to the retrospective study design, 24 hour reporting begins at the time the Investigator was informed of the event under the auspice of the clinical study. For ADE and DevD, details of the product/procedure related to the event will be included and where applicable and available, pictures taken of the device. If available the deficient product should be retained for return to S&N unless it is contaminated (e.g. used dressings must not be retained).

All SAE and ADE will be reviewed by a medically qualified person appointed by the Sponsor to determine which, if any, meet criteria for expedited reporting to the regulatory authorities. The investigator will inform the IRB/IEC of adverse events according to the IRB/IEC requirements. Depending on the nature of the adverse event, S&N may request copies of the subject's medical records, imaging, operative notes, as well as results of any relevant laboratory tests performed or

[figure not shown]
CONFIDENTIAL AND PROPRIETARY

This document contains information that is confidential and proprietary to Smith & Nephew PLC and Smith & Nephew, Inc. and is intended for use only by Smith & Nephew and its manufacturer. It shall not be reproduced or copied in whole or in part, nor shall the contents be disclosed by any means without prior written permission from Smith & Nephew, nor shall anyone make any use of it that is contrary to the expressed or implied wishes of Smith & Nephew.

Study Protocol—Device	
PMCF Study on PEEK Suture Anchors for Hip Indications	Number: 2018.14.SMD.PEEK.RET.HIP
	Version: 2.0, 03 April 2019
	Page: 48 of 63

other documentation related to the AE. If the subject was hospitalized, a copy of the discharge summary may be requested by S&N and should be forwarded as soon as it becomes available. In certain cases, S&N also may request a letter from the Investigator that summarizes the events related to the case.

Figure 1: Evaluation and Reporting of AE and DevD

CONFIDENTIAL AND PROPRIETARY

This document contains information that is confidential and proprietary to Smith & Nephew PLC and Smith & Nephew, Inc. and is intended for use only by Smith & Nephew and its manufacturer. It shall not be reproduced or copied in whole or in part, nor shall the contents be disclosed by any means without prior written permission from Smith & Nephew, nor shall anyone make any use of it that is contrary to the expressed or implied wishes of Smith & Nephew.

Study Protocol—Device	
PMCF Study on PEEK Suture Anchors for Hip Indications	Number: 2018.14.SMD.PEEK.RET.HIP
	Version: 2.0, 03 April 2019
	Page: 49 of 63

Reference the ISF Sponsor Contact Information Sheet to report SAE, unanticipated ADE and SADE, anticipated SADE, and DevD.

17. INVESTIGATOR OBLIGATIONS

The Principal Investigator will comply with the commitments outlined in the Statement of Investigator, provided by the Sponsor, and with Good Clinical Practice (GCP), and all applicable regulatory requirements as outlined in Section 26.1 of this protocol.

18. SPONSOR AND MONITOR RESPONSIBILITIES

The Sponsor will designate a monitor to conduct regular monitoring visits. The purpose of these visits are to ensure that data is accurate, complete and verifiable from source documents.

19. PROTOCOL AMENDMENTS

Amendments should be made only in exceptional cases once the study has started. Protocol amendments must be approved by the protocol signatories prior to submission to the IRB. Protocol amendments need to be approved by the IRB and Regulatory Authority (ies), as applicable prior to implementation at the site.

20. CONFIDENTIALITY OF THE STUDY

The confidentiality of this study and associated documents is governed by the terms of the Clinical Trial Agreement (CTA).

21. STATEMENTS OF COMPLIANCE

This clinical study will be performed in compliance with the ethical principles of the Declaration of Helsinki; ISO 14155: Clinical investigation of medical devices – Good Clinical Practice and ICH-E6.

CONFIDENTIAL AND PROPRIETARY

This document contains information that is confidential and proprietary to Smith & Nephew PLC and Smith & Nephew, Inc. and is intended for use only by Smith & Nephew and its manufacturer. It shall not be reproduced or copied in whole or in part, nor shall the contents be disclosed by any means without prior written permission from Smith & Nephew, nor shall anyone make any use of it that is contrary to the expressed or implied wishes of Smith & Nephew.

Study Protocol—Device	
PMCF Study on PEEK Suture Anchors for Hip Indications	Number: 2018.14.SMD.PEEK.RET.HIP
	Version: 2.0, 03 April 2019
	Page: 50 of 63

This clinical study will not commence until the required approval/favorable opinion from the IRB or regulatory authority has been obtained. Any additional requirements imposed by the IRB or regulatory authority will be followed.

Public/Products Liability Insurance has been purchased by Smith & Nephew plc. Worldwide and incorporates coverage for personal injury in respect of clinical studies. The Sponsor agrees to operate in good faith and in accordance with ABHI (Association of British Healthcare Industries) guidelines regarding compensation for injury arising in the course of clinical studies.

22. END OF STUDY

The end of study is defined as the date of the last subject, last visit (LSV). No additional care for subjects will be provided under the protocol, as this is a retrospective study.

Should circumstances arise which require the termination of the entire study prior to its planned completion (e.g. safety concerns) or circumstances arise which mean the end of the participation of an individual site (e.g. departure of Investigator, non-compliance), and then this will be undertaken according to the SOPs of the Sponsor.

23. REVISION OF THE STUDY DEVICE

If a subject has bilateral implants and has a revision, both implants will continue to be followed per the protocol visit schedule.

CONFIDENTIAL AND PROPRIETARY

This document contains information that is confidential and proprietary to Smith & Nephew PLC and Smith & Nephew, Inc. and is intended for use only by Smith & Nephew and its manufacturer. It shall not be reproduced or copied in whole or in part, nor shall the contents be disclosed by any means without prior written permission from Smith & Nephew, nor shall anyone make any use of it that is contrary to the expressed or implied wishes of Smith & Nephew.

Study Protocol—Device	
PMCF Study on PEEK Suture Anchors for Hip Indications	Number: 2018.14.SMD.PEEK.RET.HIP
	Version: 2.0, 03 April 2019
	Page: 51 of 63

24. PUBLICATION POLICY

24.1 PUBLICATION OF STUDY DATA

The preparation and submission for publication of manuscripts containing the study results shall be in accordance with a process determined by the Clinical Trial Agreements between the study Sponsor and participating institutions. The publication or presentation of any study results shall comply with all applicable privacy laws, including, but not limited to the Health Insurance Portability and Accountability Act of 1996.

